5.4. Secondary Endpoints

The secondary endpoints are:

- Change from baseline in insulin use in units per kilogram body weight per day at Week 52.
- Change from baseline in HbA1c at Week 52.
- Hypoglycemic event rates (defined as blood glucose levels of $\leq 70\text{mg/dL}$ or clinical sequelae consistent with severe hypoglycemia in the absence of a BG reading) through Week 52.

This section outlines the definition and analyses of these major secondary endpoints. Data from all subjects in full analysis set will be included and analyzed according to the randomized treatment groups.

5.4.1. Definition

5.4.1.1. Insulin use in units per kilogram body weight per day

According to the protocol, subjects are to record daily the type and amount of insulin they have used during the 7-day period immediately preceding each study visit. As the target visit date and actual visit date can be different, insulin entry is available on eDiary during a 10-day period prior

to a scheduled visit. Insulin use in units per kilogram body weight per day at a visit is calculated as the average of daily weight-adjusted total insulin usage during an 8-day period immediately preceding to a visit. A subject must have at least 3 daily insulin use records within the 8-day window prior to a visit for this calculation. Otherwise, the insulin usage will be regarded as missing for that visit.

Considering that subjects must have at least 5 days of daily insulin use recorded within the 7 days immediately preceding randomization, insulin use for a sensitivity analysis is defined. In this calculation, insulin use at a visit is calculated as the average of at least 5 days of recorded available data within 7-day period immediately preceding to the visit. If 3 or more days' data are missing during the 7-day period, then the value for that visit will be regarded missing.

5.4.1.2. Hypoglycemia event

This study uses the ADA suggested classification of hypoglycemia to guide the collection of episodes of asymptomatic and/or symptomatic hypoglycemia. Hypoglycemic events are collected through eDiary and are reviewed by investigators through hypoglycemic reconciliation form.

A hypoglycemic event is defined as either a biochemically confirmed hypoglycemic episode (ie, concurrent fingerstick glucose or plasma glucose ≤ 70 mg/dL (3.9 mmol/ L)), and/or a severe hypoglycemic event, as reported on eDiary, as follows.

- Biochemically documented hypoglycemia episode: a hypoglycemic episode with a concurrent reported glucose value of ≤ 70 mg/dL (3.9 mmol/ L), regardless of whether the episode is associated with symptoms (symptomatic hypoglycemia) or not (asymptomatic hypoglycemia).
- Severe hypoglycemic episode: a hypoglycemia episode that is considered an event requiring assistance of another person for support which may include administration of carbohydrates or glucagon. Such events do not need to have a documented blood glucose reading to be classified clinically as a severe hypoglycemic event.

Any events occurred within 1 hour are considered as one episode to avoid double-counting. The associated BG will be the minimum of those events within 1 hour. Summary and analysis of hypoglycemia events will be based on the manual algorithm.

On the hypoglycemia event reconciliation form, investigators are asked if they agree with eDiary captured hypoglycemia episode. If they agree that a hypoglycemia episode is indeed an event, then they will determine if it is a new episode or a continuation of a previous episode. This definition is applied in a sensitivity analysis of hypoglycemia event rates.

5.4.2. Analysis Methods

5.4.2.1. The change from baseline in insulin use and HbA1c at Week 52

Change from baseline in insulin use and change from baseline in HbA1c will be analyzed with an MMRM model based on a restricted maximum likelihood (REML) approach. The analysis will be based on observed data and will include the fixed, categorical effects of gender, treatment, time, and treatment-by-time interaction, as well as the continuous, fixed covariates of baseline and baseline-by-time interaction. An unstructured covariance will be used to model the within subject errors. The treatment comparisons will be made between Golimumab and placebo at Week 52 and significance tests will be based on the difference between the Least-Squares means. No missing imputation will be applied. Treatment effect in these endpoints will be estimated by the difference between the treatment groups along with their associated 95% confidence intervals.

5.4.2.2. Hypoglycemia event rate at Week 52

The number of hypoglycemia events per subject from the first study agent administration through Week 52 will be compared between treatment groups by using a Poisson regression model with treatment as fixed factor, baseline HbA1c and age as covariates, and the study participation through week 52 in logarithm as an offset variable. Hypoglycemia event rate will be estimated for each treatment group and the ratio of the rates and its 95% CI will be estimated as well.

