This sharply contrasts with the experience of adults (mid-20s and above) who often have months or years of non-specific symptoms or present asymptotically from routine glycemic screening and can often be managed for prolonged periods of time (months or years) with diet or oral hypoglycemic agents before a demonstrable insulin need. More definitive studies have shown a different rate of decline of β -cells according to age.^{14,21} Data from the Diabetes Trial Net group has demonstrated that "age is the most important factor impacting the rate of decline of C-peptide post diagnosis" and with significantly more rapid rate of decline in those 21 years old and younger versus those 22 years and older with new-onset disease.^{27,75}

These differences in disease pathophysiology between younger and older individuals with T1D are supported by the data from a number of recent new-onset T1D studies that have demonstrated differences in how younger and older individuals respond to immune interventions. Studies of abatacept, rituximab, alefacept, and teplizumab all appear to have a preferential effect on children and young adults; whereas thymoglobulin appeared to preferentially spare β -cells in those older than 21, but not in those younger.^{25,31,55,57,61,75}

Children and young adults are those at highest risk of developing disease and suffer most substantially from short- and long-term morbidity and mortality and have the most to benefit from a disease modifying therapy. The existing data suggest an age "cut-off" of approximately

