5. TREATMENT ALLOCATION AND BLINDING

Treatment Allocation

Procedures for Randomization and Stratification

Central randomization will be implemented in this study. Subjects will be randomly assigned to 1 of 2 treatment groups based on a computer-generated randomization schedule prepared before the study by or under the supervision of the sponsor. The randomization will be balanced by using randomly permuted blocks and will be stratified on subjects' baseline C-peptide AUC (<0.66 pmol/mL, ≥0.66 pmol/mL) derived from the 4-hour MMTT conducted at screening. The interactive web response system (IWRS) will assign a unique treatment code, which will dictate

the treatment assignment and matching study agent kit for the subject. Members of the study site will have unique user and personal identification numbers to contact the IWRS and must provide relevant subject details to uniquely identify the subject.

Blinding

This will be a randomized, double-blind, placebo-controlled study. To maintain the study blind, the study agent container will have a multipart label containing the study name, study agent number, reference number, and other information on each part. The label will not identify the study agent in the container. However, if it is necessary for a subject's safety, the study blind may be broken, and the identity of the study agent ascertained. The study agent number will be entered in the case report form (CRF) when the study agent is administered. The study agents will be identical in appearance and will be packaged in identical containers.

The investigative sites will not be provided with randomization codes. The codes will be maintained within the IWRS, which has the functionality to allow the investigator to break the blind for an individual subject.

Data that may potentially unblind the treatment assignment (ie, study agent serum concentrations, anti-golimumab antibodies, and treatment allocation) will be handled with special care to ensure that the integrity of the blind is maintained and the potential for bias is minimized. This can include making special provisions, such as segregating the data in question from view by the investigators, clinical team, or others as appropriate until the time of DBL and unblinding.

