11.3. Efficacy Analyses

All efficacy analyses will be performed on the mITT population unless otherwise specified. The mITT population includes all randomized subjects who have received at least 1 dose of study agent. The primary efficacy endpoint will be analyzed by using a mixed model for repeated measures (MMRM).

Primary Endpoints

The primary endpoint is the MMTT-stimulated 4-hour C-peptide AUC at Week 52. To address the primary objective of the study, the primary endpoint will be analyzed by using a MMRM based on restricted maximum likelihood. The model will be based on a normalizing transformation of $\log(\text{AUC}+1)$. The analysis will use post-baseline $\log(\text{AUC}+1)$ data as the response variable and will include the fixed, categorical effects of gender, treatment, time, and treatment-by-time interaction, as well as the continuous, fixed covariates of baseline and baseline-by-time interaction. An unstructured covariance will be used to model the within-patient errors. The treatment comparison at Week 52 in terms of the least square mean difference and the 2-sided 95% confidence interval will be estimated based on this model. Descriptive statistics and estimates from the above model will be presented on the back-transformed scale. Specifically, the back-transformed mean is the geometric-like mean derived through $\exp(y)-1$, where $y = \log(\text{AUC}+1)$. For transparency and completeness, descriptive statistics on the raw scale will be presented as well. Additional details will be presented in the SAP.

To assess the robustness of the primary analysis result, some sensitivity analyses will be conducted. Such analyses include but are not limited to the following:

1. Similar repeated measure analysis with some data imputed. If a subject's last observed AUC value prior to Week 52 is 0, then all missing values through Week 52 will be imputed with zero. Repeated measure analysis will be conducted on the partially imputed data.
2. An analysis of covariance (ANCOVA) model with $\log(\text{AUC}+1)$ at Week 52 as the response variable, baseline $\log(\text{AUC}+1)$ and age as covariates, and treatment and gender as fixed factors. Different missing data handling strategies such as completers' analysis, and multiple imputation will be explored.
3. Similar ANCOVA model by using different transformation functions.

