1.5. Randomization and Blinding

1.5.1 Randomization

Central randomization will be implemented in this study. Approximately 81 subjects who meet all enrollment criteria and have all Day 1 procedures performed will be randomly assigned to 1 of 2 treatment groups based on a computer-generated randomization schedule prepared before the study by, or under the supervision of, the sponsor. The randomization will be balanced by using randomly permuted blocks and will be stratified on subject baseline C-peptide AUC (<0.66 pmol/mL, ≥0.66 pmol/mL) derived from the 4-hour MMTT conducted at screening. The interactive web response system (IWRS) will assign a unique treatment code, which will dictate the treatment assignment and matching study agent kit for the subject. Members of the study site will have unique user and personal identification numbers to contact the IWRS and must provide relevant subject details to uniquely identify the subject.

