2.4. Definition of Subgroups

To evaluate the consistency in the key efficacy over demographics, baseline characteristics, prior and baseline medication use, subgroup analyses will be performed when sample sizes are permitted (at least 5 subjects for each treatment group within a subset). The subgroups include, but are not limited to, the following:

Baseline demographics:

- Sex (male, female)
- Baseline Age (<12, 12-18, ≥18)
- Baseline weight (<45kg, ≥45kg)

Baseline disease characteristics:

- Subjects positive to at least one diabetes-related autoantibody: 1, >1-<=3 and >3
- Baseline HbA1c categories: ≤6.5%, >6.5%
- Baseline C-peptide AUC: <0.66 pmol/mL or ≥0.66 pmol/mL
- Baseline insulin usage by quantiles
- Number of days since diagnosis of T1D: < 60 days or ≥ 60 days

In addition, subgroup analyses defined by Human Leukocyte Antigen (HLA)-DR3 presence/absence, and HLA-DR4 presence/absence will be explored for selected endpoints (See Section 5.5.2).

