5.3.2. Analysis Methods

In the primary efficacy analysis, data from all randomized subjects will be analyzed according to their assigned treatment group regardless of the actual treatment received. The primary efficacy analyses are based on the full analysis set. To address the primary objective of the study, the primary endpoint will be analyzed by using a MMRM based on restricted maximum likelihood. No missing data handling rules will be utilized for this analysis. The model will be based on a normalizing transformation of $\log(\text{AUC}+1)$. The analysis will use post-baseline $\log(\text{AUC}+1)$ as the response variable and will include the fixed, categorical effects of treatment, time, gender and treatment-by-time interaction, as well as the continuous, fixed covariates of baseline,

baseline-by-time and age. The baseline will be in $\log(\text{AUC}+1)$ scale as well. An unstructured covariance will be used to model the within-patient errors. The Kenward-Roger approximation was used to estimate denominator degrees of freedom and adjust standard errors. The treatment comparison at Week 52 in terms of the least square mean difference and the 2-sided 95% confidence interval (CI) will be estimated based on this model. Descriptive statistics and estimates from the above model will be presented on the back-transformed scale. Specifically, the back-transformed mean is the geometric-like mean derived through $\exp(y)-1$, where $y = \log(\text{AUC}+1)$. For transparency and completeness, descriptive statistics on the raw scale will be presented as well. Nominal p-values for treatment comparison will be provided for reference.

In addition, the estimated LS means of change from baseline in $\log(\text{AUC}+1)$ scale over time as well as the corresponding 60% and 95% CI from the mixed effect model will be provided by treatment group. Plot of Mean treatment difference at week 52 in change from baseline in $\log(\text{AUC}+1)$ scale will be also provided. Plot of mean 4-h C-peptide AUC by treatment group will be shown over time as well as plot of the individual 4-h C-peptide AUC over time.

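### The insulin-use and HbA1c models omit baseline C-peptide (the only stratification factor) and age: the comparison is valid, but some precision is lost if either is prognostic

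*SAP*

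**What the plan says.** SAP 5.4.2.1 lists the terms of both MMRMs: "The analysis will be based on observed data and will include the fixed, categorical effects of gender, treatment, time, and treatment-by-time interaction", with baseline and baseline-by-time as the continuous covariates. Baseline is naturally read as the endpoint's own baseline. Nothing else in the SAP or protocol adds a term. Protocol 11.3 says only that these endpoints use an MMRM and leaves the details to the SAP.

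The neighbouring text compares as follows.

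- **Stratification.** Protocol section 5 stratifies on "baseline C-peptide AUC (<0.66 pmol/mL, ≥0.66 pmol/mL) derived from the 4-hour MMTT conducted at screening", and SAP 1.5.1 repeats this. There is no other factor.
- **Primary model.** SAP 5.3.2 includes baseline log(AUC+1), which is that endpoint's own baseline, and also age ("baseline-by-time and age. The baseline will be in" the log(AUC+1) scale). The protocol's primary model (11.3) has no age term. The two secondary MMRMs therefore match the protocol template and did not receive the age term that the SAP added.
- **Third major secondary endpoint.** SAP 5.4.2.2 models hypoglycemia with a "Poisson regression model with treatment as fixed factor, baseline HbA1c and age as covariates".
- **Subgroups.** SAP 2.4 lists "Baseline C-peptide AUC: <0.66 pmol/mL or ≥0.66 pmol/mL" and age groups, and 5.4.2.3 plans forest plots. These do not adjust the main estimate.

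**The concern.** When randomisation is stratified on a variable that predicts the outcome, the arms are more alike on it than chance would make them. An analysis that leaves the variable out still estimates the treatment difference without bias. However, its residual variance contains the between-stratum variation that the design has already balanced. The reported standard error is then too large, the confidence interval too wide, and the test runs below its nominal level. Age is not a stratification factor, so omitting it costs precision without making the standard error conservative.

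There are reasons to expect some prognostic value. The sponsor chose C-peptide as the stratifier. Protocol section 1 cites data that "age is the most important factor impacting the rate of decline of C-peptide post diagnosis". The HbA1c targets to which insulin is managed also differ by age (below 7.5% up to 17 years, below 7% from 18; Protocol 3.1 and 8.1).

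Under SAP 5.2.1.1 both endpoints are formally tested, gated behind the primary and under Hochberg, with about 27 placebo subjects. Even a small loss of precision is worth recovering if that is cheap.

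**Working it through.** **1. The plan's own figure.** SAP 1.4 gives 54 and 27 subjects, SD 0.215 on log(AUC+1), and back-transformed means of 0.635 and 0.385. The difference is ln(1.635/1.385) = 0.166, or 0.166/0.215 = 0.77 SD. The noncentral t with 79 df gives 89.9% power, which reproduces the stated 90%. The documents give no SD, effect or power for insulin use or HbA1c.

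**2. Assumptions.** Let b be the partial correlation of baseline C-peptide with the Week 52 outcome beyond the endpoint's own baseline, and a the same for age. Set the residual SD after own baseline to 1. The standard error of the difference is about √(1/54 + 1/27) = 0.236. An effect of 0.66 SD gives 0.66/0.236 = 2.80, or about 80% power by the normal approximation. Neither b, a nor the 0.66 is in the documents.

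**3. Expected size.** Adding C-peptide multiplies the model standard error by √(1 − b²): 0.980, 0.954 and 0.917 at b = 0.2, 0.3 and 0.4. The interval should narrow by about 2.0, 4.6 and 8.3%, less a small charge for estimating the covariate.

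**4. Simulation, C-peptide only.** 20,000 trials per setting, N = 81, permuted blocks of 6 at 2:1 within two strata split at the C-peptide median, complete data. The model is a Week 52 ANCOVA with treatment, own baseline and sex, standing in for the Week 52 contrast of the MMRM. Tests are two-sided at nominal 0.05, before gating and Hochberg.

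| b | Power without / with | CI narrower by | Type I error without |
|---|---|---|---|
| 0.1 | 78.1 / 78.2% | 0.3% | 5.2% |
| 0.2 | 78.4 / 79.7% | 1.8% | 4.8% |
| 0.3 | 78.7 / 81.4% | 4.4% | 4.4% |
| 0.4 | 79.2 / 84.5% | 8.2% | 3.9% |

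The 5.2% is within simulation error of 5% (√(0.05 × 0.95/20,000) = 0.15 points). The estimator's true SD falls only from 0.2367 to 0.2348 (0.8%), 0.2318 to 0.2280 (1.6%) and 0.2263 to 0.2189 (3.3%) at b = 0.2, 0.3 and 0.4. The rest of the narrowing is removal of the overstated standard error. With a fixed level of 0.0167, the strictest Hochberg step for three endpoints, power at b = 0.3 goes from 63.0 to 67.3%.

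**5. Both covariates added.**

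| b, a | Power without / with both | CI width |
|---|---|---|
| 0, 0 | 78.4 / 77.6% | 1.0% wider |
| 0.1, 0.1 | 77.7 / 77.8% | about break-even |
| 0.2, 0 | 78.4 / 79.1% | – |
| 0.2, 0.2 | 77.9 / 80.5% | 3.2% narrower |
| 0.3, 0.2 | 78.4 / 82.7% | 5.8% narrower |

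At b = a = 0, the mean CI width is 0.9473 with neither term, 0.9500 with C-peptide, 0.9538 with age and 0.9566 with both. Most of the cost is therefore age (0.7% alone, against 0.3% for C-peptide, which stratification already nearly balances).

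**6. Cross-check by partial R² (= b²).** A separate simulation with 6,000 null and 4,000 alternative runs per setting gave these results for the SAP model:

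| Partial R² of C-peptide | Type I error | Mean model SE / empirical SD | Power without / with C-peptide |
|---|---|---|---|
| 0 | 4.9% | 0.99 | 77.3 / 77.0% |
| 0.05 | 4.6% | 1.01 | 79.4 / 80.7% |
| 0.10 | 4.6% | 1.04 | 78.1 / 80.8% |
| 0.20 | 3.6% | 1.07 | 78.2 / 85.1% |
| 0.30 | 3.1% | 1.10 | 79.8 / 90.4% |

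No bias appeared. With age omitted at R² 0.10, the SE ratio was 1.00 and about 4 points of power were lost, so the effect is on precision only.

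**7. By-time term.** This used a ten-visit unstructured MMRM, 2,500 trials per setting, with an assumed within-subject correlation of 0.4 + 0.6·exp(−weeks/12). If the C-peptide effect grows from 0 to b by Week 52, the by-time version narrows the interval by 4.5% (b = 0.3) and 8.2% (b = 0.4), against 3.8% and 7.0% with a main effect only. If the effect is constant, the two differ by at most 0.4 percentage points.

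**The case against.** The plan contains no error here, and the whole benefit depends on quantities that the documents do not give. If b and a are 0.1 or less, the full fix gains nothing or loses slightly.

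The evidence for age is thin. The protocol's statement concerns C-peptide decline rather than insulin use or HbA1c, and the contrast it reports is 21 and younger against 22 and older, while this trial randomises ages 6 to 21. The protocol's reason for stratifying is that response to therapy may depend on baseline function, which is effect modification rather than prognosis. Titrating insulin to HbA1c targets could weaken a link between C-peptide and HbA1c, so a single b for both endpoints is doubtful.

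The consistency argument is also limited. The primary model contains C-peptide only because it is that endpoint's own baseline, and the hypoglycemia model omits C-peptide too.

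Finally, the power figures come from complete-data ANCOVA. The MMRM check covers interval width only, without dropout, in a model whose unstructured covariance already has 10 × 11/2 = 55 parameters. The stricter-level figures are fixed-alpha powers, not Hochberg powers, and ignore gating.

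All of this stands as a limit on size and certainty. It does not remove the point. Adjusting for the randomisation factor is the ordinary default, and for C-peptide the cost of being wrong is about 0.1 point of power.

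**Conclusion.** The concern holds, as a small efficiency point on two gated secondary endpoints. The planned comparison is valid. If baseline C-peptide has a partial correlation of 0.2 to 0.3 with the outcome, the SAP models give up about 1 to 3 points of nominal power, report intervals about 2 to 4% wider than needed, and test at 4.4 to 4.8% rather than 5%. Losses of about 7 to 11 points require a partial R² of 0.2 to 0.3, which nothing in the documents supports. Below about b = a = 0.1 there is no gain.

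These figures assume complete data, 81 subjects at 2:1 and a 0.66 SD effect. The direction is the same at 0.5 SD (54.5 to 58.3% at b = 0.3, C-peptide only) and 0.78 SD (90.1 to 91.8%). Dropout was not simulated. Validity with missing data rests on missingness at random given the modelled terms. If missingness depends on C-peptide or age, that is a further, unquantified reason to include them.

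**What to change.** Before Week 52 unblinding, add three terms to both MMRMs in SAP 5.4.2.1: baseline log(AUC+1), its interaction with time, and age as a continuous covariate. This is the covariate form of the SAP primary model in 5.3.2. State the by-time choice explicitly. If only one covariate is added, use C-peptide, because it is the stratification factor and costs almost nothing if it proves uninformative. If the sponsor prefers the present models, a sentence giving the reason would do. After unblinding, the adjusted models could serve only as labelled supportive analyses.

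The cost is one sentence of SAP text, no new data, and about one degree of freedom per covariate at Week 52. If neither covariate is prognostic, adding both loses about 0.8 points of power (78.4 to 77.6%) and widens the interval by about 1.0%. C-peptide alone costs about 0.1 point and 0.3%. Protocol 11.3 need not change.

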4. Comparing change from baseline in 4-hour C-peptide AUC directly by using non-parametric method such as rank analysis of covariance or ANCOVA model if the normality assumption holds.

Subgroup analysis of the primary endpoint by selected baseline characteristics will be presented. Details will be outlined in the SAP.

Secondary Endpoints

The major secondary endpoints listed below will be analyzed without multiplicity adjustment. Treatment effect in these endpoints will be estimated by the difference between the treatment

groups along with their associated 95% confidence intervals. The hypoglycemia event rate (number of hypoglycemia episodes per patient-year exposure) at Week 52 will be analyzed using a Poisson regression model. Change from baseline in insulin use and change from baseline in HbA1c will be analyzed by using an MMRM model. Additional details will be provided in the SAP.

1. Change from baseline in insulin use in units per kilogram body weight per day at Week 52.
2. Change from baseline in HbA1c at Week 52.
3. Hypoglycemic event rates (defined as BG levels of ≤ 70 , 55, and 35 mg/dL or clinical sequelae consistent with severe hypoglycemia in the absence of a BG reading) through Week 52.

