17. ADMINISTRATIVE REQUIREMENTS

17.1. Protocol Amendments

Neither the investigator nor the sponsor will modify this protocol without a formal amendment by the sponsor. All protocol amendments must be issued by the sponsor and signed and dated by the investigator. Protocol amendments must not be implemented without prior IEC/IRB approval, or when the relevant competent authority has raised any grounds for non-acceptance, except when necessary to eliminate immediate hazards to the subjects, in which case the amendment must be promptly submitted to the IEC/IRB and relevant competent authority. Documentation of amendment approval by the investigator and IEC/IRB must be provided to the sponsor. When the change(s) involves only logistic or administrative aspects of the study, the IEC/IRB (where required) only needs to be notified.

During the course of the study, in situations where a departure from the protocol is unavoidable, the investigator or other physician in attendance will contact the appropriate sponsor representative listed in the Contact Information page(s), which will be provided as a separate

document. Except in emergency situations, this contact should be made before implementing any departure from the protocol. In all cases, contact with the sponsor must be made as soon as possible to discuss the situation and agree on an appropriate course of action. The data recorded in the CRF and source documents will reflect any departure from the protocol, and the source documents will describe this departure and the circumstances requiring it.

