5.2.1.1. Multiplicity Adjustment for Testing Procedures

To control for multiplicity in the primary endpoint analysis and major secondary endpoint analyses, the hypothesis testing will be conducted in a hierarchical manner with the test on the primary analysis first and the tests on major secondary analyses next. The success of any major secondary analysis, i.e., $p\text{-value} < 0.05$, is contingent upon the success of the primary statistical analysis. Hochberg approach will be applied within major secondary endpoint analyses.

Nominal p-values will be reported for all other efficacy endpoints.

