5.2.3. General Analysis Method

Data summaries will be provided for each treatment group. Statistical comparisons will be made between active and placebo treatment groups.

Descriptive statistics such as mean, median, standard deviation, minimum, and maximum will be used to summarize continuous variables. Counts and percentages will be used to summarize categorical variables. Recurrence data will be summarized by mean as well as counts and percentages. Median will be reported for time to event variables. Graphical data displays (e.g., mean plots, Kaplan-Meier curves, and forest plots) will be used to support the presentation of data.

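### The hypoglycemia rate ratio (SAP 5.4.2.2) comes from a Poisson model with no allowance for overdispersion, so its 95% CI can be too narrow

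*SAP*

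**What the plan says.** SAP 5.4.2.2 compares the number of events per subject from first dose through Week 52. The counts are "compared between treatment groups by using a Poisson regression model with treatment as fixed factor, baseline HbA1c and age as covariates", with the log of time in study as an offset, and "the ratio of the rates and its 95% CI will be estimated as well". Protocol 11.3 says the rate "will be analyzed using a Poisson regression model" and closes that paragraph with "Additional details will be provided in the SAP".

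SAP 5.4 lists this rate among the major secondary endpoints. Under SAP 5.2.1.1, success on any of them "is contingent upon the success of the primary statistical analysis", and "Hochberg approach will be applied within major secondary endpoint analyses". Protocol 11.3 instead says the major secondaries get no multiplicity adjustment.

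Three other provisions bear on the counts:
- SAP 5.4.1.2 counts any episode with glucose at or below 70 mg/dL, with or without symptoms, and severe episodes. It merges events less than an hour apart.
- The only sensitivity analysis for this endpoint (also SAP 5.4.1.2) replaces the event definition with the investigator-reconciled one.
- SAP 5.2.3 adds a descriptive rule: "Recurrence data will be summarized by mean as well as counts and percentages".

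No section names a scale parameter, a robust variance, a negative binomial alternative or a check for overdispersion.

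**The concern.** Each subject contributes one count. With no variance method named, the natural reading is ordinary Poisson regression, in which the variance of that count equals its mean given treatment, baseline HbA1c and age.

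The documents describe differences between subjects that the model does not contain. Protocol 9.8 sets a floor of four glucose checks a day and allows more as needed or on suspicion of hypoglycemia, so a subject who tests more will record more episodes. Protocol 8.1 allows insulin by injection or by pump. The offset corrects only for follow-up time, and the one-hour merge removes only duplicates within a subject.

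If such variation remains after the covariates, the standard error of the log rate ratio is understated. The first consequence is the published CI, which is reported whether or not the gate opens and which the gate cannot protect. The forest plots of major secondary endpoints in SAP 5.4.2.3 would carry the same fault if built on this model. The second is the p-value entering the Hochberg step, a procedure that presumes each p-value is valid.

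**Working it through.** **Inputs from the documents.** 54 golimumab and 27 placebo subjects (SAP 1.4); two-sided 0.05 (SAP 5.2.1); the model and offset of SAP 5.4.2.2; the gate and Hochberg step of SAP 5.2.1.1. The plan gives no power, rate or dispersion figure for hypoglycemia. Its 90% power concerns the primary endpoint. It reproduces (difference ln 1.635 − ln 1.385 = 0.1659, SD 0.215, noncentral t on 79 df: 89.9%) but does not bear on this point.

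**Assumed.** Mean events per subject-year, and k, the variance of the subject-level rate multiplier left after covariates (k = 0 is true Poisson).

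**Formula.** The count variance is mean + k × mean² = mean × (1 + mean × k). The true standard error is therefore f = sqrt(1 + mean × k) times the Poisson one. Coverage of the nominal 95% CI is 2Φ(1.96/f) − 1.

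**Worked case, mean 5, k = 0.25, full follow-up.**
- Poisson SE of the log rate ratio: sqrt(1/(54 × 5) + 1/(27 × 5)) = sqrt(1/270 + 1/135) = 0.1054.
- A rate ratio of 1.00 is reported as exp(±1.96 × 0.1054) = 0.81 to 1.23.
- f = sqrt(1 + 5 × 0.25) = 1.50, so the correct interval is exp(±1.96 × 0.1581) = 0.73 to 1.36.
- With an assumed 10% early dropout, simulation gives 0.81 to 1.24 against 0.72 to 1.38.

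**Simulation of the SAP model.** No treatment effect; gamma-Poisson counts; age and baseline HbA1c both generating the counts (assumed log-rate effect 0.15 per SD each) and fitted; log-time offset with 10% dropout; t reference on 77 df for the corrected tests. Size and Hochberg figures use 6,000 runs per cell; coverage uses a separate 4,000. The Hochberg column is the false declaration rate for hypoglycemia with the gate open and no effect on any of the three secondaries, treated as independent.

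| Mean, k | f: formula / simulated | Poisson CI coverage %: formula / simulated | Size of 5% test, %: Poisson / Pearson / HC3 | Hochberg false declaration, %: Poisson / Pearson / HC3 |
|---|---|---|---|---|
| 1, 0.1 | 1.05 / 1.06 | 93.8 / 94.1 | 5.4 / 4.4 / 3.9 | 1.9 / 1.4 / 1.2 |
| 2, 0.25 | 1.22 / 1.23 | 89.0 / 87.8 | 10.5 / 4.8 / 4.3 | 4.9 / 1.6 / 1.4 |
| 5, 0.25 | 1.50 / 1.51 | 80.9 / 81.4 | 18.7 / 5.5 / 4.6 | 10.7 / 1.9 / 1.6 |
| 15, 0.5 | 2.92 / 2.92 | 49.9 / 49.6 | 49.9 / 6.0 / 4.9 | 40.9 / 2.2 / 1.9 |

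A correctly sized test gives about 1.7% in the last column. Of the Poisson false declarations, 1.1, 2.6, 5.4 and 20.6 percentage points are in the direction of benefit. If insulin use and HbA1c are both won, Hochberg tests hypoglycemia at the full 5%, and the size column becomes the upper bound.

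**Wider range.** A simpler two-group simulation without covariates (40,000 runs per cell) gives Poisson size near 5% at k = 0 for every mean tried. At mean 20 it gives 25.9% for k = 0.1 and 55.7% for k = 0.5.

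**Corrected variance.** Over 13 (mean, k) cells of the SAP-model simulation, with means 1 to 15 and k 0 to 1, size is 4.3% to 6.1% with Pearson scaling and 3.9% to 5.5% with HC3, both against t. At k = 0 the CI is 1.01 times (Pearson) or 1.04 times (HC3) the Poisson width.

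**The case against.** The SAP is silent on the variance rather than wrong about it: a scaled or robust Poisson model is still a Poisson model, so the text arguably already permits the fix. That is true, but it leaves the choice open until the data are seen, and software defaults give the unscaled version.

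The size of the problem comes from outside the documents. The assumed cells run from trivial to extreme, and nothing in the plan says which applies. Care is partly standardised (a sponsor-supplied meter, a minimum check frequency, common HbA1c targets), and age and baseline HbA1c are in the model. This stands. The mechanism is certain, the magnitude is not, and the figures are illustrations rather than predictions.

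Decision impact is limited. This is a Phase 2a trial of 81 subjects, and the primary C-peptide conclusion cannot be touched. Through Hochberg, a falsely small hypoglycemia p-value can ease the thresholds for insulin use and HbA1c, but only slightly: each one's false declaration rate rises from 1.7% to 1.8% at (5, 0.25) and to 2.1% at (15, 0.5). This also stands. It argues against calling the fault critical, not against repairing it.

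Finally, the gate exists only in the SAP. Under Protocol 11.3, with no multiplicity adjustment, the unadjusted size column applies directly. The two texts should be reconciled.

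**Conclusion.** The concern holds. As written, SAP 5.4.2.2 gives a rate-ratio CI and p-value that are valid only if no between-subject variation in hypoglycemia rate remains after age and baseline HbA1c. Otherwise the interval is too narrow by about sqrt(1 + mean × k). Over the four assumed cells this means coverage from about 94% down to about 50%. Under the SAP's gate and Hochberg rules, with no true effect on any of the three secondaries, false declarations run from 1.9% to 40.9%, against about 1.7% for a correctly sized test. If the counts are truly Poisson given the covariates, the planned interval is valid. Because the documents cannot settle which case applies, a variance method that holds in both should be named in advance. The rate-ratio estimate and the models for the primary endpoint, insulin use and HbA1c are unaffected. This should be fixed, but it does not threaten the trial's main conclusion.

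**What to change.** Add one sentence to SAP 5.4.2.2 before the Week 52 unblinding. Keep the Poisson mean model, its covariates and the log-time offset; base the standard error, 95% CI and p-value of the rate ratio on an HC3-type sandwich variance with a t reference; and carry that p-value into the Hochberg step. Pearson-scaled (quasi-Poisson) standard errors with a t reference are an equal choice. Name one, and use it in the SAP 5.4.2.3 forest plots too.

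No new data are needed. The cost is a CI about 4% wider (HC3) or 1% wider (Pearson) if there is no dispersion. If there is, the CI widens by about f, as it should.

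Protocol 17.1 states that "Neither the investigator nor the sponsor will modify this protocol without a formal amendment by the sponsor". A robust or scaled Poisson model is still the model Protocol 11.3 names, and that section defers details to the SAP, so neither needs an amendment. Negative binomial regression would also be acceptable statistically, but it is not the model the Protocol names and would raise the amendment question. That makes the robust or scaled Poisson the simpler route.
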